6.4 Non-Serious AEs

A non-serious AE is any event that results in minimal transient impairment of a body function or damage to a body structure and does not require any intervention listed under the criteria for “Serious Adverse Event.” Nonserious adverse events require routine reporting via EDC.

6.5 Anticipated AEs

An anticipated AE is one that has been reported in previous studies of RF ablation and can be anticipated in this current study as per the risk analysis. Table 6-2 provides a comprehensive list of anticipated AEs.

Table 6-2 Anticipated Adverse Events

Anticipated Adverse Events	
1.	Acute Respiratory Distress Syndrome (ARDS)
2.	Air embolism
3.	Allergic reaction
4.	Anaphylactic shock
5.	Anemia
6.	Allergic reaction to Anesthesia (e.g., hair loss)
7.	Apnea - sedation induced
8.	Arrhythmia: bradycardia
9.	Arrhythmia: tachycardia
10.	Arrhythmia: pro-arrhythmias
11.	Arrhythmia: ventricular tachyarrhythmia / pro-arrhythmia
12.	Aspiration pneumonia
13.	Asthmatic attack
14.	Atelectasis
15.	Atrial fibrillation
16.	Exacerbation of pre-existing arrhythmia
17.	Atrio-Esophageal fistula
18.	Atypical left atrial flutter
19.	AV fistula
20.	Bleeding complications
21.	Bleeding requiring transfusion
22.	Cardiac arrest
23.	Cardiac perforation
24.	Tamponade
25.	Cardiac thrombo-embolism
26.	Cerebro-vascular accident (CVA) / stroke
27.	Chest pain/discomfort
28.	Complete heart block, temporary or permanent
29.	Conduction block: ongoing / resolved
30.	Congestive Heart Failure
31.	Coronary artery dissection
32.	Coronary artery occlusion
33.	Coronary artery spasm
34.	Coronary artery Thrombosis
35.	Death
36.	Deep venous thrombosis
37.	Dislodgement of ICD (Implantable Cardioverter Defibrillator)
38.	Dislodgement of permanent pacing leads
39.	Disseminated Intravascular Coagulation
40.	Dyspnoea
41.	Endocarditis
42.	Epistaxis

Anticipated Adverse Events	
43.	Expressive aphasia
44.	Fainting
45.	Fatigue
46.	Gastro-intestinal NOS
47.	Gastric reflux
48.	Nausea
49.	Gastrointestinal diverticulosis
50.	Heart Failure
51.	Hematoma (local) /ecchymosis
52.	Hemorrhage
53.	Hemothorax
54.	High / increased creatine phosphokinase (CPK)
55.	Hypotension
56.	Hypoxia
57.	Infection, localized
58.	Infection, systemic
59.	Laceration
60.	Leakage of air or blood into the lungs or other organs due to perforation
61.	Liver toxicity
62.	Mobile strands in Inferior Vena Cava
63.	Myocardial Infarction
64.	Neurological disorders (tremor)
65.	Neurological disorders (poor coordination)
66.	Neurological disorders (headache)
67.	Obstruction to the vascular system
68.	Perforation to the vascular system
69.	Damage to the vascular system
70.	Pericardial effusion resulting in tamponade
71.	Pericardial effusion without tamponade
72.	Pericarditis
73.	Peripheral embolus
74.	Peripheral nerve injury
75.	Peripheral thromboembolism
76.	Phlebitis
77.	Phrenic nerve damage
78.	Diaphragmatic paralysis
79.	Pleural effusion
80.	Acute Respiratory Distress Syndrome (ARDS)
81.	Pneumothorax
82.	Pseudoaneurysm
83.	Pulmonary edema
84.	Heart failure

Anticipated Adverse Events	
85.	Pulmonary embolism
86.	Pulmonary hypertension
87.	Pulmonary toxicity, like acute pulmonary syndrome
88.	Pulmonary vein dissection
89.	Pulmonary vein Stenosis
90.	Pulmonary vein thrombus
91.	Pump failure
92.	Renal failure
93.	Respiratory depression
94.	Respiratory failure
95.	Retroperitoneal hematoma
96.	Rhabdomyolysis, including produced by body position or Propofol
97.	Sedation induced CO2 retention with lethargy and cholecystitis
98.	Seizure
99.	Sepsis
100.	Skin burns (due to cardioversion, tape, etc.)
101.	Skin discoloration
102.	Skin injury / muscle or connective tissue injury due to body position, electrical cardioversion
103.	Skin rash
104.	Thrombocytopenia
105.	Thromboembolism
106.	Thrombosis
107.	Thyroid disorders
108.	Transient extremity numbness
109.	Transient ischemic attack (TIA)
110.	Unintended complete or incomplete AV, Sinus node, or other heart block or damage
111.	Urinary retention
112.	Urinary tract infection
113.	Urinary tract injury or infection related to the urinary catheter
114.	Valvular damage/insufficiency
115.	Vasovagal reactions
116.	Vision change
117.	Volume overload
118.	Worsening obstructive, restrictive, or other form of pulmonary disease
119.	X-ray radiation injury of skin, muscle and/or organ

6.6 Unanticipated Serious Adverse Device Effect

A (serious) adverse device effect (ADE/SADE) is any (serious) adverse effect on subjects' health, safety, rights, welfare, and life-threatening problems including death, which is caused by, or associated with the study device. Accordingly, relationship to device or study is crucial assessment by investigators. An unanticipated adverse device

effect (UADE) or unanticipated serious adverse device effect (USADE) is any ADE or SADE that has not been previously identified in nature, severity, or degree of incidence in the investigational plan or risk analysis report.

6.7 Clinical Investigation Device Failure/Malfunction/Deficiency

A device has failed if it does not perform according to the instructions for use or fails to meet the expectations of the device and/or investigator (i.e., related to appearance of the device, performance, durability, safety, effectiveness, quality, reliability, labeling, etc.). If a device failure is detected or suspected, it should be documented on the appropriate CRF and **the device must be promptly returned** according to the Sponsor's instructions. If the device failure is associated with an AE, **both** the device failure and AE must be reported to the Sponsor **immediately** upon awareness (refer to section 6.8).

6.8 Reporting Requirements

All SAEs, UADE/SADE/USADE, and Study device failure/malfunction/deficiency, whether or not they are related to the device or procedure, **must be reported by eCRF** to the Sponsor (**Biosense Webster Clinical Operations**). Investigators/sites are expected to report any SAEs, UADE/SADE/USADE, and Study device failure/malfunction/deficiency immediately upon their awareness of the event, or in any event no later than 72 hours from the time of awareness. Failure to report any event requiring expedited reporting within this interval will be classified as a protocol deviation.

For all other non-serious AEs, the Study Site has 14 calendar days from when the site becomes aware to inform the Johnson and Johnson Study Sponsor by entering the AE into the eCRF.

6.9 Intensity or Severity

Intensity (or severity) of AEs is defined as follows:

Table 6-3 Intensity or Severity Definitions

Mild	Events that result in minimal transient impairment of a body function or damage to a body structure, and/or does not require intervention other than monitoring.
Moderate	Events that result in moderate transient impairment of a body function or damage to a body structure, or that require intervention, such as the administration of medication, to prevent permanent impairment of a body function or damage to a body structure.
Severe	Events that are life threatening and/or result in permanent impairment of body functions or damage to body structures, or that require significant intervention, such as major surgery, to prevent permanent impairment of a body function or damage to a body structure.

Intermittent AEs should be classified according to their greatest severity. A continuous AE that changes severity should be reported as a new AE.

6.10 Outcome

AE outcomes are assessed according to the following classifications:

Table 6-4 Adverse Event Outcome Classifications

Resolved without Sequelae	Subject fully recovered with no observable residual effects.
Resolved with Sequelae	Subject recovered with observable residual effects.
Ongoing	Adverse event has not resolved and additional change in condition is possible
Death	Subject died as a result of the adverse event, whether or not the AE is related to the device or procedure. Note; deaths from any cause occurring on this study are to follow expedited reporting.

6.11 Causality

Cause of AEs is defined as follows:

Table 6-5 Adverse Event Causality Classifications

Device Relationship	
Definitely Device-Related	The THERMOCOOL SMARTTOUCH® SF catheter directly caused or contributed to the AE.
Possibly Device-Related	The THERMOCOOL SMARTTOUCH® SF catheter may have caused or contributed to the AE.
Not Device-Related	The AE is not associated with the THERMOCOOL SMARTTOUCH® SF catheter.
Procedure Relationship	
Definitely Procedure-Related	The AE is directly associated by timing and/or pathophysiology with the standard electrophysiology or AF ablation procedure described in this protocol.
Possibly Procedure-Related	The AE may be associated by timing and/or pathophysiologic with the standard electrophysiology procedure described in this protocol.
Not Procedure Related	The AE is not associated with the AF procedure described in this protocol.

6.12 Documentation

All AEs must be documented on the appropriate eCRF. All AEs must be monitored until they are adequately resolved or stabilized, with follow-up reports submitted to the Sponsor or designee as soon as new information becomes available. Additional documentation may be requested by the Sponsor or designee, such as a written event narrative detailing the

clinical course, copies of correspondence with the local IRB/EC, hospital records, death certificates, and autopsy reports, if applicable.

6.13 Global Safety Monitoring Committee (GSMC)

In order to minimize risks to subjects enrolled in the study, the sponsor will convene a formal independent Global Safety Monitoring Committee (GSMC) at pre-determined intervals to review the adverse event reports and recommend appropriate action(s) to ensure subject safety.

Primary Adverse Events and Serious Adverse Events occurring within 30 days of the ablation procedure and of cardiac origin will be reviewed by Biosense Webster clinical staff with Medical Safety Officer or designee, and submitted to the independent GSMC for review.

7.0 STATISTICAL ANALYSIS METHODS

7.1 Analysis Population

- **Modified Intent-To-Treat (mITT) Population:** the modified Intent-To-Treat (mITT) population will consist of all enrolled subjects who meet all eligibility criteria **AND** in whom
 - (1) RF energy was delivered with study catheter **OR**
 - (2) Study catheter was inserted but no RF energy was delivered.
- **Safety Population (SP):** The safety population will consist of all enrolled subjects who have undergone insertion of the study catheter.
- **Per Protocol (PP) Population:** The PP population will include subjects who satisfy the following criteria:
 - are enrolled and meet all eligibility criteria
 - have undergone RF ablation
 - are treated with the study catheters, and have been treated for the study-related arrhythmia

7.2 Analyses for Primary Endpoints

7.2.1 Analyses for Primary Effectiveness Endpoint

The null and alternative hypotheses are:

Hypothesis $H_0: P_E \leq 0.40$

$H_a: P_E > 0.40$

P_E : the freedom from documented atrial fibrillation, atrial flutter and atrial tachycardia recurrence at 15 months follow-up

Null hypothesis: The freedom from documented AF/AFL/AT at 15 months is less than or equal to the pre-determined performance goal of 40%.

Alternative hypothesis: The freedom from documented AF/ATL/AT at 15 months is greater than the pre-determined performance goal of 40%.

Analysis Population: The per-protocol population will be used as the primary analysis population. Subjects with missing effectiveness endpoints data during 15 months follow-up period will be excluded from the primary analysis. The subjects who have failed the primary effectiveness endpoint before 15 months will be included in the analysis. Analyses of the primary effectiveness endpoint will be repeated in the mITT population. Sensitivity analyses for missing data will be performed in the PP and mITT populations to assess the impact of missingness on the primary effectiveness outcome and are described in the Statistical Analysis Plan (SAP).

Analysis Method: The primary effectiveness endpoint will be evaluated using the exact test for a binomial proportion at a two-sided significance level of 5%. If the lower bound of the exact two-sided 95% confidence interval of the primary effectiveness endpoint rate is greater than the performance goal of 40%, the study will be considered to have demonstrated effectiveness.

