3.0 STUDY DESIGN

The PRECEPT study is a prospective, multicenter, non-randomized clinical evaluation utilizing the THERMOCOOL SMARTTOUCH® SF catheters in treating subjects with symptomatic PsAF who have failed at least one antiarrhythmia drug. Up to 367 subjects will be enrolled at up to 35 sites (approximately 30 US and 5 OUS). Effectiveness and safety endpoints have been defined, and will be compared to predetermined performance goals. Subjects who sign the PRECEPT informed consent are considered enrolled in the study. Enrolled subjects who satisfy all eligibility criteria will then undergo the ablation procedure with the study catheter. After the study ablation procedure, subjects will enter a 3-Month Medication Adjustment Period followed by a 3-Month Therapy Consolidation Period (Day 0-180).

The first 3 months after the ablation procedure, (Medication Adjustment Period; Day 0-90) is intended to allow for modifications to the subject’s medication and allow substrate remodeling to occur. Medication adjustment includes dose modification of currently used AAD or adding new AAD. The following 3-month period (Therapy Consolidation Period; Day 91-180), is to assess the status of the Medication Adjustment Period and perform repeat ablations as necessary. Cardioversion is allowed if the AF recurrence persists during the Therapy Consolidation Period.

After the Therapy Consolidation Period, subjects will enter the Evaluation Period (Days 181-450). Subjects having AF recurrence and/or receiving therapeutic interventions during the evaluation period will be considered effectiveness failures (refer to Section 4.1.1 for all effectiveness failure modes).

All subjects will undergo follow up visits at defined intervals (refer to Table 5-1 Schedule of Treatments and Evaluations). Subjects complete the PRECEPT study after the 15-month follow up visit.

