3.2 Subject Disposition

- **Enrolled Subjects:** subjects who sign the informed consent.
- **Excluded Subjects:** subjects who are enrolled but never undergo insertion of the study catheter.
- **Discontinued Subjects:** subjects who have the investigational catheter inserted but do not undergo ablation (i.e., no RF energy is delivered via the study device). These discontinued subjects will be followed up for 30 days.
- **Lost to Follow-up Subjects:** subjects who are enrolled and have study catheter inserted, but contact is lost after most recent follow-up visit (despite 3 documented attempts).
- **Withdrawn / Early Termination Subjects:** subjects who withdraw consent for study participation or are withdrawn by the investigator or are terminated from the study prior to completion of all follow-up visits.
- **Completed Subjects:** enrolled subjects who completed the 15-month follow-up visit.

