7.4 Primary Effectiveness Endpoint

Based on a performance goal of 40% and an anticipated freedom from AF recurrence of 50%, 330 subjects will be required to obtain at least 90% power at a two-sided significance level of 0.05 using the exact binomial method.

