7.6 Total Sample Size

It is estimated that the attrition rate is no more than 10%. In order to obtain 330 subjects, Biosense Webster proposes to enroll 367 ($=330/0.90$) subjects to account for this potential subject attrition.

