##### *1) Best-Case Scenario*

Subjects with missing effectiveness outcome will be treated as effectiveness success. The point estimate for freedom from recurrence of atrial tachyarrhythmias and the exact two-sided 95% confidence interval will be presented.

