##### *3) Multiple Imputation*

Multiple imputations will be used to impute missing data for the effectiveness outcome. A multivariate logistic regression model incorporating the demographic and baseline characteristics will be used to impute missing values for the primary effectiveness outcome. Five imputed datasets will be generated. The imputed datasets will then be combined to incorporate both within- and between imputation variability.

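### Does keeping dropouts who have already failed, while deleting event-free dropouts, bias the primary success rate enough to require a change?

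*Protocol*

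**What the plan says.** Protocol 7.2.1 sets two rules for the per-protocol primary analysis. The first is deletion: "Subjects with missing effectiveness endpoints data during 15 months follow-up period will be excluded from the primary analysis". The second is retention: "The subjects who have failed the primary effectiveness endpoint before 15 months will be included in the analysis". SAP 10.4.1 repeats the first rule but not the second. SAP section 1, however, states that its methods are based on section 7.0 of the protocol, where the second rule stands.

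On sample size, Protocol 7.4 states that "330 subjects will be required to obtain at least 90% power at a two-sided significance level of 0.05 using the exact binomial method", for 50% against a goal of 40%. Protocol 7.6 adds "It is estimated that the attrition rate is no more than 10" per cent and inflates 330 to 367. Those 367 are consented subjects (Protocol 3.0: "Subjects who sign the PRECEPT informed consent are considered enrolled in the study"). The 10% must therefore also cover the group that Protocol 3.2 calls excluded: "subjects who are enrolled but never undergo insertion of the study catheter".

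For missing outcomes, SAP 10.4.3.1 plans best case, worst case, multiple imputation and tipping point in both the PP and mITT populations. It also plans a comparison of subjects with and without missing data. SAP 10.4.5.2 plans a Kaplan-Meier analysis of AF/AT/AFL recurrence in both populations, with censoring.

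**The concern.** Whether a dropout enters the analysis depends on that subject's outcome. If dropout is unrelated to outcome, such a rule over-represents failures and biases the estimate downward.

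The planned sensitivity analyses do not obviously supply a corrected figure. Best and worst case are bounds, and the tipping point tests the conclusion without estimating the rate. The imputation model is described thus: "A multivariate logistic regression model incorporating the demographic and baseline characteristics will be used to impute missing values for the primary effectiveness outcome". It is fitted to the same selected subjects and ignores the time a dropout had already spent event-free, so it carries essentially the same bias.

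A Kaplan-Meier estimate would use that time. However, SAP 10.4.5.2 names only recurrence as the event. It does not say whether the other failure modes in SAP 6.1.1 count, how they are dated, or when event-free dropouts are censored. At stake would be a primary rate reported slightly too low, some lost power, and no clearly defined estimate to show by how much.

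**Working it through.** **The plan's own figures.** The exact rule at 330 subjects requires at least 151 successes. Type I error is then 1.93% and power at 50% is 94.5%, so the claim of at least 90% is true. 330/0.90 rounds up to 367, as stated.

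**Formula.** Let S be the true success rate and d the proportion dropping out after ablation, uniformly over Day 0-450 and independently of outcome. A success is deleted with probability d. A failure at day T is deleted only if dropout comes first, which has average probability d x f, where f = E[T]/450. Hence

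expected rate = S(1 - d) / [S(1 - d) + (1 - S)(1 - d f)].

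**Assumed timings (not in the documents).**
- Failures uniform over Day 181-450: f = 315.5/450 = 0.701.
- Failures front-loaded (Day 180 plus an exponential with mean 60 days, capped at Day 450): f = 239.3/450 = 0.532.
- With 15% of failures at Day 0, each f is multiplied by 0.85, giving 0.596 and 0.452.

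**Worked case.** S = 0.50, d = 0.10, f = 0.701: 0.450 / (0.450 + 0.50 x 0.9299) = 0.450/0.915 = 49.2%.

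The number analysed is binomial, and successes given that number are binomial at the expected rate. The chance of passing can therefore be computed exactly.

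| Scenario | f | Expected rate, true 50% | Power | False pass, true 40% |
|---|---|---|---|---|
| (a) 367 ablated, d = 10% | 0.701 | 49.2% | 91.6% | 1.0% |
| | 0.596 | 48.9% | 90.1% | 0.8% |
| | 0.532 | 48.7% | 89.1% | 0.7% |
| | 0.452 | 48.5% | 87.7% | 0.5% |
| (b) 349 ablated, d = 5% | 0.701 | 49.6% | 93.6% | 1.5% |
| | 0.596 | 49.5% | 93.0% | 1.4% |
| | 0.532 | 49.4% | 92.7% | 1.2% |
| | 0.452 | 49.3% | 92.2% | 1.1% |
| (c) 330 ablated, no later dropout | any | 50.0% | 94.5% | 1.9% |

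The outer bound at 10% has every failure before any dropout: 0.45/(0.45 + 0.50) = 47.4%. If all dropout falls before Day 181 and all failures after it, the bias is zero.

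**Other planned analyses, scenario (a), no Day 0 failures.** Worst case is 0.50 x 0.90 = 45.0%. Best case is 0.50 + 0.50 x 0.10 x f = 53.5% (uniform) or 52.7% (front-loaded). In simulation, baseline-only imputation gives 49.3% or 48.8%, and a Kaplan-Meier estimate of the full composite gives 50.0%.

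**If dropout depends on outcome.** The planned rule is unbiased when failures leave 1/f times as often as successes: 1.43 (uniform) or 1.88 (front-loaded), and 1.68 or 2.21 with 15% Day 0 failures. Beyond that the bias is upward. In simulation at 1.43 and 1.88, the composite Kaplan-Meier overstates a true 50% as 50.7% and 51.0%.

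With 13.3% of failures and 5% of successes leaving at a true 40% (0.6 x 13.3 + 0.4 x 5 = 10% overall), the planned rule passes falsely in 5.6% (uniform) or 3.5% (front-loaded) of trials. A Kaplan-Meier rule does so in 8.5% or 6.4% (simulated).

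**Reading SAP 10.4.5.2.** It sits within SAP 10.4, the primary endpoint analyses. SAP 10.6.2 separately plans a Kaplan-Meier analysis of Day 181-450 recurrence, and Protocol 4.3 sets the other failure modes aside for that endpoint. In SAP 10.4.3.1 recurrence already stands for the primary outcome, as in the best-case text: "The point estimate for freedom from recurrence of atrial tachyarrhythmias and the exact two-sided 95% confidence interval will be presented". The composite reading is therefore plausible, though not certain.

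**The case for a change.** The strongest case for a change is that the asymmetry is real, its direction under independent dropout follows from algebra, and the remedy would be SAP wording with no new data. Two analysts could draw different curves from SAP 10.4.5.2. SAP 10.4.1, read alone, could lead someone to delete a subject who failed and then left. That would raise the rate if failure prompts leaving. In the least favourable timings of scenario (a), power falls to 87.7%, below the 90% sought.

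The asymmetry and the missing detail stand. The rest carries less weight:

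- A better-defined Kaplan-Meier estimate recovers none of that power, because the exact binomial test would still decide.
- Scenario (a) needs all 367 consented subjects to be ablated, although the 10% must also cover those never treated.
- Kaplan-Meier rests on its own untestable assumption. It is the more liberal of the two exactly where missing data threaten the conclusion, when failures leave more often. The worst-case and tipping-point analyses address that situation, and both are planned.
- SAP 10.4.1 omits the retention sentence but does not contradict it, and the SAP takes its methods from the protocol section that contains it.

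**Conclusion.** No change follows. If dropout is unrelated to outcome, the rule understates the success rate by 0 to about 1.5 points under the main timing assumptions, and by 2.6 points at the outer bound. These figures assume a true rate of 50% and at most 10% attrition, with dropout and failure times that the documents do not give. In that setting the test is conservative: false-pass rates in the table are 0.5% to 1.9%, below 2.5%. Power is 92% or more if half or more of the attrition precedes ablation, and 88% to 92% if all of it follows.

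If failures leave more often, the bias shrinks and, beyond a ratio of 1.43 to 2.21, reverses. The planned rule can then pass too easily, but the Kaplan-Meier alternative would do so more, and the planned worst-case and tipping-point analyses cover that risk. The event, dating and censoring in SAP 10.4.5.2 are details an analyst can fill sensibly from SAP 6.1.1. Stating them would leave the primary rate, the test and the decision as they are.
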